## 7.4.1 Adverse Events

### 7.4.1.1 Adverse Event Definitions

#### Adverse Event

An AE is any untoward medical occurrence in a subject or clinical investigation subject administered a pharmaceutical product, regardless of causal relationship with this treatment. An AE can therefore be any unfavorable and unintended sign (including an abnormal laboratory finding), symptom, or disease temporally associated with the use of a medicinal product, whether or not considered related to the medicinal product.

For surgical or diagnostic procedures, the condition/illness leading to such a procedure is considered as the AE rather than the procedure itself.

The Investigator is required to grade the severity or toxicity of each AE.

Investigators will reference the NCI-CTCAE 4.03 (publication date: 14 June 2010), a descriptive terminology that can be used for AE reporting.

A general grading (severity/intensity; hereafter referred to as severity) scale is provided at the beginning of the above referenced document, and specific event grades are also provided.

If a particular AE's severity is not specifically graded by the guidance document, the Investigator is to use the general NCI-CTCAE definitions of Grade 1 through Grade 5 following his or her best medical judgment.

The 5 general grades are:

- Grade 1 or Mild
- Grade 2 or Moderate
- Grade 3 or Severe
- Grade 4 or Life-threatening
- Grade 5 or Death

According to Sponsor convention, any clinical AE with severity of Grade 4 or 5 must also be reported as an SAE. However, a laboratory abnormality of Grade 4, such as anemia or neutropenia, is considered serious only if the condition meets one of the serious criteria described below.

If death occurs, the primary cause of death or event leading to death should be recorded and reported as an SAE. “Fatal” will be recorded as the outcome of this specific event and death will not be recorded as separate event. Only, if no cause of death can be reported (for example, sudden death, unexplained death), the death per se might then be reported as an SAE.

Investigators must also systematically assess the causal relationship of AEs to study treatment (M4112, CCI [REDACTED] using the following definitions. Decisive factors for the assessment of causal relationship of an AE to the study treatment include, but may not be limited to, temporal relationship between the AE and the study treatment, known side effects of study treatment, medical history, concomitant medication, course of the underlying disease, study procedures.

**Unrelated:** Not reasonably related to the IMP. The AE could not medically (pharmacologically/clinically) be attributed to the study treatment under study in this clinical study protocol. A reasonable alternative explanation must be available.

**Related:** Reasonably related to the IMP. The AE could medically (pharmacologically/clinically) be attributed to the study treatment under study in this clinical study protocol.

### **Abnormal Laboratory Findings and Other Abnormal Investigational Findings**

Abnormal laboratory findings and other abnormal investigational findings (for example, on an ECG trace) should not be reported as AEs unless they are associated with clinical signs and symptoms, lead to treatment discontinuation or are considered otherwise medically important by the Investigator. If a laboratory abnormality fulfills these criteria, the identified medical condition (for example, anemia, increased ALT) must be reported as the AE rather than the abnormal value itself.

### **Adverse Drug Reaction (ADR)**

ADRs are defined in this study as any AEs suspected to be related to study treatment by the Investigator and/or Sponsor.

## SAE

An SAE is any untoward medical occurrence that at any dose:

- Results in death
- Is life-threatening (Note: The term “life-threatening” refers to an event in which the subject is at risk of death at the time of the event, not an event that hypothetically might have caused death if it was more severe)
- Requires inpatient hospitalization or prolongs an existing hospitalization
- Results in persistent or significant disability or incapacity
- Is a congenital anomaly or birth defect
- Is otherwise considered to be medically important.

Note: important medical events that may not result in death, be life-threatening, or require hospitalization may be considered as SAEs when, based upon appropriate medical judgment, they may jeopardize the subject or may require medical or surgical intervention to prevent one of the outcomes listed above. Examples of such events include allergic bronchospasm requiring intensive treatment in an emergency room or at home, blood dyscrasias or convulsions that do not result in inpatient hospitalization, or the development of drug dependency or drug abuse.

For the purposes of reporting, any suspected transmission of an infectious agent via an IMP is also considered an SAE, as described in Section [7.4.1.5](#).

### Events that Do Not Meet the Definition of an SAE

Elective hospitalizations to administer, or to simplify study treatment or study procedures (for example, an overnight stay to facilitate therapy and related hydration therapy application) are not considered SAEs. However, all events leading to unplanned hospitalizations or unplanned prolongation of an elective hospitalization (for example, undesirable effects of any administered treatment) must be documented and reported as SAEs.

### Events Not to Be Considered as AEs/SAEs

Medical conditions present at the initial study visit that do not worsen in severity or frequency during the study are defined as baseline medical conditions, and are not to be considered AEs.

### AE/SAEs Observed in Association with Disease Progression

Progression of the disease/disorder being studied assessed by measurement of lesions on radiographs or other methods as well as associated clinical signs or symptoms (including laboratory abnormalities) should not be reported as an (S)AE, unless the subject's general condition is more severe than expected for the subject's condition and/or unless the outcome is fatal within the AE reporting period (as defined in Section [7.4.1.3](#)).

### **Predefined AESIs for Safety Monitoring**

Any AE that is suspected to be a potential irAE and infusion related reactions will be considered an AESI.

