Subjects treated with M4112 should also be monitored for potential irAEs, which may first manifest after weeks of treatment. Such events may consist of persistent rash, diarrhea and colitis, autoimmune hepatitis, arthritis, glomerulonephritis, cardiomyopathy or uveitis and other inflammatory eye conditions. Risk management guidance is provided in Section 6.5.5.3.

No embryo-fetal toxicity study have been performed to date, therefore effects on pregnancy cannot be excluded, pregnancy and lactation are excluded from the study. Highly effective contraception must be used for men and women of childbearing potential (Section 5.3.1 and Section 5.3.2).

**Liver toxicity and irAEs will be considered AESIs for M4112 requiring expedited reporting from the Investigator to the Sponsor within 24 h of learning of its occurrence.**

CCI

CCI

CCI

Instructions for treatment interruption/discontinuation or modification of infusion-related reactions/hypersensitivity will be provided to investigators as well as guidance for medical management (Table 8).

CCI [REDACTED]. Inclusion criteria for the study will require adequate entry hemoglobin value. Respective hematological parameters will be monitored every week during the 1st cycle of dose escalation phase. Treatment modification, interruption, and discontinuation rules, depending on severity, will be provided. CCI [REDACTED]

CCI

CCI

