- Any Grade  $\geq 3$  clinical signs and symptoms related to increased QTc
- Evidence of hepatocellular toxicity attributable to study drug, such as increase in AST or ALT  $\geq 5$ -fold ULN for at least or  $\geq 3 \times$  ULN elevation of ALT or AST and elevation of serum total bilirubin to  $\geq 2 \times$  ULN, without initial findings of cholestasis (elevated serum ALP) or other apparent clinical causality (eg, viral hepatitis A, B, C, or co-medication).

If the above criteria are met, subjects should undergo close observation, including monitoring for symptoms (clinical signs of hepatitis, hypersensitivity, fatigue, decreased appetite, nausea, vomiting, abdominal pain, jaundice, fever, or rash) and hepatic function (AST, ALT, ALP and fractionated bilirubin) at least every 3 days, until symptoms and/or hepatic function abnormalities resolve, stabilize or return to baseline values. This event should be reported to the Sponsor within 24 h of learning of its occurrence.

Subjects experiencing DLTs during the DLT observation period (applicable for Part I only) as described in Section 6.2.4 will not receive further protocol therapy. Subjects with nausea and vomiting will maintain normal schedule without re-dosing.

In addition, any immune-related toxicity event observed in the next cycle will be reviewed and taken into account by the SMC for the overall evaluation of the safety and proposal of dose escalation of M4112 **CCI**.

All subjects treated in dose escalation cohorts who miss > 5 planned total daily doses of M4112 **CCI** in the first cycle (first 28 days) of the dose escalation part for other than safety reasons are not eligible for DLT assessment, will not be considered in the Bayesian model, and will not formally be replaced.

The MTD is defined by the SMC. An MTD is suggested from the Bayesian logistic regression model with target toxicity of 30%.

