### **AESIs**

Comprehensive assessment of any apparent toxicity experienced by each subject will be performed from the time of giving informed consent and throughout the study. The Investigator will report any AESI, whether observed by the Investigator or reported by the subject. The AESI reporting period for safety surveillance begins when the subject is initially included in the study (date of first signature of informed consent) and continues until last Safety Follow-up Visit defined as  $30 \pm 3$  days or  $90 \pm 6$  days (as a phone call) after the last dose of M4112, **CCI** or before start of any anticancer therapy, whatever comes first.

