### 15.2 Adverse Events

The severity of AEs will be graded using the NCI-CTCAE v4.03. If a particular AE's severity is not specifically graded by this guidance, the Investigator uses the general NCI-CTCAE definitions of Grade 1 through Grade 5 following his or her best medical judgment. The latest MedDRA version at the time of data cut-off will be used to code AEs according to System Organ Class (SOC) and Preferred Term (PT).

- **Treatment Emergent Adverse Events (TEAEs)** are events with onset dates occurring during the on-treatment period, or those that worsen in severity during the on-treatment period. All analyses will be based on TEAEs unless otherwise specified.
- **Related Adverse Events** have a relationship to study treatment of “Related” as reported by the Investigator on the Adverse Events CRF page, or unknown (i.e., no answer to the question “Relationship M4112”).
- **Serious Adverse Events (SAEs)** are those recorded on the Adverse Events CRF page as Serious Adverse Event = “Yes”.
- **Adverse Events Leading to Treatment Discontinuation** are those recorded on the Adverse Events CRF page as Action(s) taken with M4112 = “Drug withdrawn”.
- **Adverse Events Leading to Dose Modifications** are those recorded on the Adverse Events CRF page as Action(s) taken with M4112 = “Dose reduced”.
- **Adverse Events Leading to Treatment Interruption** are those recorded on the Adverse Events CRF page as Action(s) taken with M4112 = “Drug interrupted”.
- **Adverse Events Leading to Death** are those recorded on the Adverse Events CRF page as Outcome = “Fatal” as well as AEs of Grade 5.
- **Adverse Events of Special Interest (AESIs)** for M4112 include liver toxicities and immune-related AEs (irAEs) / autoimmune disorders. Any AESI is indicated as such by the Investigator on the Adverse Events CRF page and is also reported as an SAE.

Incomplete AE-related dates will be handled as follows:

- In case the onset date is missing completely or missing partially but the onset month and year, or the onset year are equal to the start of study treatment then the onset date will be replaced by the minimum of start of study treatment and AE resolution date.
- In all other cases the missing onset day or missing onset month will be replaced by 1.

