### 15.3.3 Adverse Events of Special Interest

A listing of all AESIs will be provided, sorted by SOC and PT, including: AE, SOC, PT, relationship to M4112, planned dose level, time since last and since first administration of M4112, and subject's age, sex, and race (also see [Section 15.2.1](#)).

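### Protocol 7.4.1.1 leaves liver toxicity out of the predefined AESIs although Protocol 3.4.2.1 and SAP 15.2 include it, so non-immune hepatic events could be missed from the AESI outputs

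*Protocol*

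**What the plan says.** Three places define AESIs.

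- Protocol 7.4.1.1, under the heading that predefines them: "Any AE that is suspected to be a potential irAE and infusion related reactions will be considered an AESI".
- Protocol 3.4.2.1, closing the description of M4112's potential risks: "Liver toxicity and irAEs will be considered AESIs for M4112 requiring expedited reporting from the Investigator to the Sponsor within 24 h".
- SAP 15.2 (the Integrated Analysis Plan), which says that AESIs "for M4112 include liver toxicities and immune-related AEs (irAEs) / autoimmune disorders".

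Protocol 7.4.1.4 gives the AESI reporting duty, "The Investigator will report any AESI, whether observed by the Investigator or reported by the subject". It neither redefines the term nor repeats the 24-hour limit.

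For the analysis, SAP 15.2 states: "Any AESI is indicated as such by the Investigator on the Adverse Events CRF page and is also reported as an SAE". SAP 15.2.1 puts AESIs among the frequency tables, and SAP 15.3.3 adds: "A listing of all AESIs will be provided, sorted by SOC and PT". The appended plan for the Safety Monitoring Committee (SMC) shows AESIs in the patient profiles (16.1), the overall AE summary table (17.1.1) and a listing (17.2.2). Its AE definitions in 17.1 do not say what an AESI is.

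**The concern.** The definition placed among the AE definitions differs from the one the SAP says it is reporting. The difference falls on liver toxicity, which Protocol 3.4.2.1 describes as a clinically significant potential risk seen in animal studies. Because the SAP relies on the Investigator's mark alone, nothing downstream would correct a narrower reading at a site.

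What is at stake is how the AESI table can be read. A row showing no hepatic AESIs could mean that none occurred or that none were marked, and the outputs would not distinguish the two. The same uncertainty would reach the SMC while it advises on dose escalation. The 24-hour reporting that Protocol 3.4.2.1 attaches to AESIs could also be missed for such events.

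The SAP sentence about SAEs is a second inconsistency. The protocol defines seriousness by outcome criteria (7.4.1.1) and nowhere says that an AESI is automatically an SAE.

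**Working it through.** No arithmetic applies to the definitions, so the passages are compared step by step.

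**1. What each definition covers**

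| Source | irAEs | Liver toxicity | Infusion-related reactions |
|---|---|---|---|
| Protocol 3.4.2.1 | yes | yes | not named |
| Protocol 7.4.1.1 | yes (suspected potential irAEs) | not named | yes |
| SAP 15.2 | yes, with autoimmune disorders | yes | not named |

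**2. Does the irAE wording bring liver toxicity in?** Only in part. Protocol 3.4.2.1 numbers the potential risks. Liver toxicity is item 2, attributed to liver hypertrophy or direct lesions; immune-related and autoimmune events are item 5. On immune-related events the same section says: "Such events may consist of persistent rash, diarrhea and colitis, autoimmune hepatitis, arthritis, glomerulonephritis, cardiomyopathy or uveitis". The irAE management table in Protocol 6.5.5.3 also has a hepatic part that starts at Grade 1. Hepatic events therefore split into two groups:

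- suspected to be immune-related: an AESI under all three texts;
- not suspected to be immune-related: an AESI under Protocol 3.4.2.1 and SAP 15.2, but not under Protocol 7.4.1.1.

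The second group is the exposed one, and it matches the mechanisms given for risk item 2.

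**3. From flag to output.** SAP 15.2 takes AESI status from the CRF. Neither SAP 15.2.1 nor 15.3.3 names another source. The SMC plan names no source either; I assume it uses the same CRF flag.

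**4. Does the hepatocellular reporting rule close the gap?** No. Protocol 6.2.4 says of hepatocellular toxicity above its enzyme limits: "This event should be reported to the Sponsor within 24 h of learning of its occurrence". Section 6.2.3 has a parallel rule. Neither calls the event an AESI, so the thresholds do not decide whether the flag is set. A non-immune event could go unmarked above them as well as below.

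**5. Outputs that do not use the flag.** TEAE tables by SOC and PT, with related and Grade 3 or higher versions (SAP 15.2.1); laboratory grade shifts and the plot of peak ALT against peak bilirubin (SAP 15.4); and the DLT analysis (SAP 15.1), whose criteria include hepatocellular toxicity. Exposed hepatic events remain visible in these.

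**6. Size.** Let H be the number of hepatic events, i the share suspected to be immune-related, and f the share of the remainder that sites mark anyway. The number missed is H × (1 − i) × (1 − f). The documents give none of the three, so the result lies anywhere from 0 to H × (1 − i).

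**7. The SAE clause.** SAP 15.2 also defines SAEs as events whose CRF seriousness field is yes. Read literally, the AESI sentence conflicts with that rule for a non-serious AESI, such as a Grade 1 hepatic irAE that meets no seriousness criterion.

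**The case against.** The case on the other side is substantial and limits the point.

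- **Sites are told elsewhere.** Protocol 3.4.2.1 is part of the same document and instructs Investigators to report liver toxicity as an AESI within 24 hours. Protocol 7.4.1.2 sends sites to the eCRF Completion Guidelines, which are not among the documents. How the flag was explained to sites is unknown. This stands: an under-count is possible, not established. That sites work from 7.4.1.1 is itself an inference from its place among the AE definitions.
- **The exposed group is narrow.** A mere suspicion of an immune cause brings a hepatic event into 7.4.1.1. This stands, but it does not remove the group whose injury is judged direct or due to hypertrophy.
- **Infusion-related reactions.** A reader might infer that listing them is a mistake for an oral drug. The documents do not support that: the protocol also covers combination parts with infusions (7.1.2). The SAP covers Part IA only, so leaving them out there is expected.
- **SAE counts.** A reader might infer that the SAP sentence inflates them. The same section takes SAEs from the CRF seriousness field, and no programming rule counts AESIs as serious. The protocol also uses the SAE form for expedited reports that need not be serious, as with overdose (6.12). What stands is a wording inconsistency.
- **Investigator flagging is a prespecified method**, and the protocol does not require a MedDRA list. That is true, but a flag is only as good as the definition behind it, and here the definitions differ.

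**Conclusion.** The contradiction is established by the text. Protocol 7.4.1.1 does not name liver toxicity as an AESI; Protocol 3.4.2.1 and SAP 15.2 do. The consequence is conditional: hepatic events not suspected to be immune-related could be absent from the AESI table, the AESI listing and the SMC's AESI outputs. It rests on two assumptions, that some sites apply 7.4.1.1 alone and that the unseen eCRF guidance does not correct this.

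The size cannot be derived. One subject is 1/24 = 4.2% of the roughly 24 planned and 1/3 = 33.3% of a three-subject cohort. A reader might take these as the expected error, but they only give the weight of one hypothetical missed case. Nor do the documents support a reading that hepatic toxicity would go unreported. The effect is confined to the AESI outputs and, possibly, the 24-hour AESI notification. The correction is still worth making, because liver toxicity is a named risk in a first-in-human study.

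**What to change.** 1. Reconcile Protocol 7.4.1.1 with Protocol 3.4.2.1 and SAP 15.2 so that liver toxicity is named as an AESI for M4112. Infusion-related reactions can stay for the combination parts. Repeat or cross-refer to the definition in Protocol 7.4.1.4 and in the SMC plan.
2. In the SAP, prespecify a MedDRA list of hepatic and immune-related terms. Check the CRF flag against it before database lock and raise discrepancies at the data review meeting that SAP Section 6 already requires. Report both the flagged and the list-derived AESIs. This also works on data already collected.
3. Reword the SAP 15.2 sentence on SAEs so that it agrees with the protocol's seriousness criteria and the SAP's own CRF-based definition. If it was meant to describe an expedited reporting route, say so.

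The cost is wording changes, one term list and a little programming. More events may be shown as AESIs, and some list-derived events will be ones the Investigator did not regard as of special interest, which is why the two counts should be kept separate.

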#### **7.4.1.2 Methods of Recording and Assessing Adverse Events**

At each study visit, the subject will be queried on changes in his or her condition. During the reporting period, any unfavorable changes in the subject's condition will be recorded as AEs, whether reported by the subject or observed by the Investigator.

Complete, accurate, and consistent data on all AEs experienced for the duration of the reporting period (defined below) will be reported on an ongoing basis in the appropriate section of the eCRF. All SAEs must be additionally documented and reported using the appropriate SAE eCRF page as described in Section 7.4.1.5.

It is important that each AE report include a description of the event, its duration (onset and resolution dates [and times when it is important to assess the time of AE onset relative to the recorded treatment administration time]), its severity, its causal relationship with the study treatment, any other potential causal factors, any treatment given or other action taken, including dose modification or discontinuation of the study treatment, and its outcome. In addition, serious cases should be identified and the appropriate seriousness criteria documented.

Specific guidance can be found in the eCRF Completion Guidelines.

#### **7.4.1.3 Definition of the Adverse Event Reporting Period**

The AE reporting period for safety surveillance begins when the subject is initially included in the study (date of first signature of informed consent) and continues through the  $30 \pm 3$  days Safety Follow-up Visit or  $90 \pm 6$  days Safety Follow-up Visit (for Part IB and Part IC; as a phone call). After the Safety Follow-up Visit all SAEs and treatment-related nonserious AEs need to be documented up until stabilization or until the outcome is known, unless the subject is documented as "lost to follow-up".

Any SAE assessed as related to IMP must be reported whenever it occurs, irrespective of the time elapsed since the last administration of IMP.

#### **7.4.1.4 Procedure for Reporting Serious Adverse Events, Adverse Events of Special Interest, and Dose Limiting Toxicities**

##### **SAEs**

In the event of any new SAE occurring during the reporting period, the Investigator must immediately (within a maximum of 24 h after becoming aware of the event) inform the Sponsor or its designee using the SAE Report Form in the eCRF following specific completion instructions.

In exceptional circumstances, an SAE (or follow-up information) may be reported by telephone; in these cases, an SAE Report Form in the eCRF must be completed immediately thereafter. Names, addresses, and telephone and fax numbers for SAE reporting will be included in the study-specific SAE Report Form.

Relevant pages from the eCRF may be provided in parallel (for example, medical history, concomitant drugs). Additional documents may be provided by the Investigator, if available (for example, laboratory results, hospital report, autopsy report).

The Investigator must respond to any request for follow-up information (for example, additional information, outcome, final evaluation, other records where needed) or to any question the Sponsor/designee may have on the AE within the same timelines as those noted above for initial reports. This is necessary to ensure prompt assessment of the event by the Sponsor or designee and (as applicable) to allow the Sponsor to meet strict regulatory timelines associated with expedited safety reporting obligations.

Requests for follow-up will usually be made via the responsible monitor, although in exceptional circumstances the Drug Safety department of the Sponsor may contact the Investigator directly to obtain clarification or to obtain further information or to discuss the event.

